4.3 Inclusion and Exclusion Criteria

4.3.1. Inclusion and Exclusion Criteria for Patients

Table 2. Eligibility Criteria
Inclusion Criteria

• Female• Age \geq 18 years• Diagnosis of any stage (I-IV) gynecologic cancer (uterine, ovarian, cervical, vaginal/vulvar, fallopian tube, peritoneal)• Receiving any treatment for gynecologic cancer or have completed acute treatment < 10 years ago• Attending clinic visits in the course of follow-up care (i.e., not an initial consult visit)
Exclusion Criteria

• Not able to speak English• Eastern Cooperative Oncology Group (ECOG)⁸² Performance score > 2• Overt cognitive dysfunction or psychiatric disturbance or severe mental illness (e.g., dementia, suicidal behavior, or psychosis), as observed or judged by the researcher or referring source.

Our decision to include women with any gynecologic cancer in as opposed to restricting it to women with a cancer of a specific tumor site is guided by findings from prior studies demonstrating similar types of sexual concerns and lack of communication among women in these groups, and is informed by the design of numerous research studies in this area.^{6,12,15,28} We choose to include women across a range of stages of disease, those who are in active treatment as well as who have completed treatment, and who are either partnered or unpartnered because women across all of these categories report sexual concerns and are in need of relevant interventions, are similarly likely to report low rates of sexual health communication,^{23,24,81} and are willing to participate in such trials.³⁰ Although we anticipate that women with sexual problems will self-select into the study,⁸³ as in our previous trial of STC, we do not limit participation by the presence/severity of sexual problems because women could have reason to discuss sexual concerns with their clinician other than for seeking management of sexual difficulties (e.g., to inquire about the safety of sexual activity while undergoing chemotherapy).⁸⁴ However, we will collect information to examine this. During screening, women will be assessed for access to an electronic device (e.g., smartphone, tablet, computer); women assigned to STC without such access will be able to use a study laptop to watch the video.

Because gynecologic cancer affects individuals who are biologically female, we do not include biological males in the current study. For simplicity, the term “women with gynecologic cancer” is used in describing the study population. However, we will assess self-identified gender, and will not exclude individuals who identify as male while being treated for a gynecologic cancer (i.e., as in the case of trans men, who may identify as men yet can still be diagnosed with a disease of the female genital tract if these organs are intact). Considering that communication of sexual health can be especially fraught for individuals who are of a sexual or gender minority,⁸⁵⁻⁸⁷ including such individuals in our study could help us determine whether the STC intervention is generalizable to this underserved population.

4.3.2 Inclusion and Exclusion Criteria for Clinicians

Clinician participants will be gynecologic oncology clinicians or radiation oncologists treating gynecologic cancer patients (physicians, advanced practice clinicians). They will be identified through direct contact by [name] (Co-I) or by the PI ([name]), or through staff or clinical meetings.

4.4 Screening

Patients. Patients who do not contact the study team to opt out after receiving the recruitment letter will be called by the research assistant to conduct a telephone screening or may be approached in person (i.e., in the FCCC clinic), who will review the study procedures, risks, benefits, and emphasize to patients that their decision to participate will not affect their care. Screening will assess accessibility of computer/devices, and will include a brief assessment of health-related quality of life (e.g., level of sexual concerns, pain, fatigue), and offer a detailed discussion of the study procedures. Recruitment tracking will be done using a combination of password-protected Excel files and REDCap forms. For women who opt out prior to completing screening (e.g., leave us a voicemail saying they do not want to enroll, or refuse over the phone before screening is undertaken), we will collect and retain minimal information (i.e., name, study status) that will allow us to refrain from contacting them again with regard to the study and thus respecting their wishes. Minimal information related to sexual dysfunction issues will be retained for possible grant submission. This information may guide the study design in the future. This information may reveal that patients without any symptoms are less likely to agree to participate. This is considered preparatory to research and will not be used for any purpose other than to guide a future proposal.

Clinicians. All clinicians will be identified in advance as appropriate for the study, negating the need for formal screening procedures.

5.0 Consent Process

For clinicians, consent forms will be presented at that time of contact about the study; Informed consent documents will be presented via paper or web (i.e., REDCap) consents according to the clinicians' preferences.

We have utilized similar online consent processes in multiple patient and provider studies. For patients, consent will occur primarily using a subject specific REDCap form, which will be obtained prior to patients' completion of baseline surveys, which are also online.

For patients who are unable to complete online consents, they will be given the option of signing paper consents either in person or via mail.

All participants will be given the opportunity to ask questions about the study and their involvement prior to consent, and all candidates will be ensured that their participation is voluntary and will not affect their care (if patients) or employment (if providers) at Fox Chase. Only English speakers will be enrolled, so there will not be any consent forms in other languages. No children or minors will be enrolled.

6.0 Measures and Self-Report Data Collection

6.1. Clinician Measures. Clinician self-report data include socio-demographic and clinical self-report items (e.g., length of time in practice, clinical role) and are collected at the time of consent.

6.2. Patient Measures. Patients will complete self-report surveys immediately after enrolling (baseline; T1), at an in-person clinic encounter with their gynecologic cancer clinician several weeks after receiving the intervention materials (post-intervention; T2), and at 2-month follow-up (T3). Self-report data collection will generally be completed using REDCap, a secure, HIPAA-compliant web-based application used successfully in multiple trials in our lab, with paper-and-pencil versions available for those who lack computer access. T2 surveys, which are completed in-clinic immediately following the clinic encounter, will be paper-and-pencil. For patients who are unable to stay in-person to complete their paper survey, online versions of the form will be sent via email to the patient for completion using a link to the online survey with instructions for the patient to complete the survey as soon as possible. Medical data will be gathered through chart review by a qualified member of the research team.

Aim 1. Aim 1 measures include those pertaining to the feasibility and acceptability of the STC intervention in women with gynecologic cancer.

Feasibility will be measured through measures of participant enrollment, defined as the percent of eligible candidates approached who enroll, retention to study completion, defined as completion of all study surveys, and rates of intervention completion, defined by self-report responses on the program evaluation.

Acceptability of the STC intervention will be measured through self-report program evaluation survey administered at post-intervention (after clinic encounter). The main items considered outcomes for this aim are: intervention satisfaction, informativeness, helpfulness, relevance, ease of participation, approval of the format, likelihood of recommending to others, and perceived importance of the program for people with gynecologic cancer. Other items in the program evaluation will assess other aspects of the intervention and may include open-ended items to gather further information that could be useful in improving the intervention content for the larger trial.

Aim 2. Aim 2 measures include self-report outcome measures that will help assess preliminary effects of the STC intervention on patient-clinician communication (beliefs about sexual health, communication behaviors), and on patients' sexual and psychological health outcomes, as shown in Table 3, as well as standard socio-demographic and clinical data collected at baseline through self-report or medical chart review. Self-report surveys will be administered at three time points: Baseline, occurring at the time of consent; Post-intervention (T2), occurring immediately following the clinic encounter; and 2-month

Follow-Up (T3), occurring 2-months after the clinic encounter. Self-report outcome surveys carry an estimated response burden of no more than 30 minutes. Measures of covariates and other study surveys are estimated to take < 10 minutes. **Table 3 below** shows self-report measures used to assess outcomes and a schedule of assessment time points.

Patient-Clinician Communication. Self-Efficacy for Communicating about Sexual Health. Two items assess patients' self-efficacy (confidence) for communicating with their gynecologic cancer clinician about sexual health concerns in terms of either talking (item 1) or asking (item 2) about sexual health. Response options use an 11-point scale (0=not at all confident to 10=extremely confident). Mean scores will be used. Self-efficacy items were developed according to social cognitive theory guidelines^{59,88} with input from a trans-disciplinary team, were used successfully in similar studies,^{89,90} and had excellent reliability (Cronbach's alpha $\geq .97$).⁹¹ Patients' Communication Behaviors. Patients' clinical communication about sexual health will be assessed via self-report measure completed immediately following the patient's T2 clinic encounter, and will be assessed as the proportion of clinic encounters in which the patient reports (1) discussing any sexual concerns with her clinician, (2) raising the topic of sexual health, and (3) asking a question pertaining to sexual health. Analyses of data from our previous trial of the STC intervention in women with breast cancer showed a high kappa coefficient between dialogue coded for discussions of sexual concerns and patients' self-report of discussing a sexual health topic (kappa = .71), suggesting that using self-report to collect the communication data is appropriate. Further, in our prior work, we have found that when sexual health concerns are salient for patients, as they will likely be for most participants, patients tend to be more accurate in their self-reports of sexual health communication during a clinic encounter.⁹² As in our previous work,^{30,36} the self-report assessment about sexual health will assess whether following topics are discussed, whether the patient raised the topic, and whether the patient asked about any of these topics: sexual activity, function (desire, arousal, orgasm, pain/discomfort), intimate relationships, general sexual concerns, or body image.

Sexual and Psychological Health Outcomes. Sexual activity will be assessed using the PROMIS sexual activity screener item, obtained from the PROMIS SexFS Brief Profile Version 2.0,^{91,93,94} which has significant data supporting its validity in women with cancer. This screener assesses any sexual activity (partnered or unpartnered; examples are "masturbation, oral sex, and intercourse") within the past 30 days. Sexual function will be assessed using the 19-item Female Sexual Function Index (FSFI).⁹⁵ The FSFI is a widely used comprehensive sexual function measure with established validity in women with cancer,⁹⁶⁻⁹⁸ which assesses biological, psychological, and social dimensions of women's sexual experiences including desire, arousal, pain, and satisfaction with sexual activity.^{76,99,100} Total scores, reflecting women's overall sexual function, capture increases in response to participation in behavioral (non-medical) sexual function intervention trials in women with cancer^{76,101} and will be used. Psychological distress is measured by the Hospital Anxiety and Depression Scale anxiety (HADS-A) and depressive symptoms (HADS-D) subscales.¹⁰² Both subscales have had good reliability in prior studies (Cronbach's alpha=.86 and .83, respectively).

Exploratory Aim and Other Measures. The exploratory aim assesses any associations between patients' partnered status or initial sexual concerns score and feasibility, acceptability, and preliminary effects of the STC intervention. Socio-demographic characteristics, such as age, race/ethnicity, sexual orientation, education, socio-economic status, and partnered status will be assessed using the baseline (T1) survey. Patients' sexual concerns will be assessed using a standard item from the Patient Care Monitor, which will be assessed during screening, along with other PCM items (e.g., pain, fatigue, vaginal dryness). These items are assessed using a 0-10 scale and have proven valid and informative in our prior research.^{36,92} Clinical variables including stage of disease, tumor site, and dates and types of surgeries and medical treatments will be obtained using medical records. In addition, we will also assess patients' use of sexual

aids (e.g., vaginal health aids such as lubricant or moisturizer) using a validated item from the PROMIS SexFS, as an exploratory measure that could help us determine whether assessing this in the larger trial makes sense. Ultimately, if patients' communication about sexual health is successful, they may employ sexual aids and we want to capture this. Body Compassion. We will assess body compassion, a concept denoting acceptance and compassion toward the physical body, using five items comprising the Acceptance Subscale of the Body Compassion Scale,³⁴ at baseline. There is growing research suggesting that body image concerns including body compassion are predictors of psychosocial health outcomes for women with gynecologic cancer.¹² Therefore, we will include this measure at baseline to obtain exploratory data that we may use to generate hypotheses for future studies. Medical comorbidity for patients will be obtained by the Self-Administered Comorbidity Questionnaire (SCQ)¹⁰³. In addition to these measures, we will obtain information from patients at the time of screening on health concerns, including sexual concerns, pain, and fatigue, using validated items from the Patient Care Monitor. These items are scored using a 0-10 scale and we have found them to be highly valid in our prior research.

Table 3. Patient Aim 2 Study Self-Report Outcome Measures	Baseline	Post-Intervention	2-Month Follow-up
Measure			
Patient-Clinician Communication (Primary)			
Self-efficacy (Beliefs) ⁸⁸	X	X	X
Communication Behaviors (Discuss, Raise Topic, Ask a Question) ⁹²	-	X	-
Patient Sexual and Psychological Health Outcomes (Secondary)			
Sexual Activity (PROMIS-SexFS Sexual Activity Screener) ^{91,93,94}	X	-	X
Female Sexual Function Index (FSFI) ⁹⁵	X	-	X
HADS-Anxiety (HADS-A) ¹⁰²	X	-	X
HADS-Depression (HADS-D) ¹⁰²	X	-	X
Other Measures (Exploratory)			
Socio-Demographics	X	-	-
Health-Related Quality of Life (HRQOL)	X	X	-
Sexual Aids (PROMIS SexFS) ⁹³	X	-	X
Body Compassion Scale – Acceptance Subscale ³⁴	X	-	-
Self-Administered Comorbidity Questionnaire (SCQ)	X	-	-
Program Evaluation	-	X	-

7.0 Randomization

Randomization will occur once the patient has consented and completed the baseline (T1) survey. Using a similar approach as was used successfully in our prior breast cancer trial, patients will be randomized with an allocation ratio of 2:1 to either the STC intervention (video, workbook, and resource guide) or control condition (resource guide only). The statistician ([name]) will generate the randomization sequences using an automated randomization procedure in REDCap that limits prediction of allocation and protects masking of allocations. The automated randomization function in REDCap will inform the Research Lab Manager of the patient's assigned treatment condition. Randomization in blocks of six will guarantee that, after every six assignments, the study arms will have equal numbers.

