4.2 Recruitment and Reimbursement

Patients. In all, between 30 and 36 patients with gynecologic cancer will participate. Using methods we have employed in previous studies, potentially eligible patients will be identified from consented provider's clinic schedules. This pre-identification process involves pre-screening of patients using their medical records on major characteristics (e.g., length of time since treatment, ECOG score) to reduce unnecessary burden of contacting patients who will not screen in or who may be ill. The research assistant will ask the providers' permission to approach patients identified as medically eligible. If the provider approves, a letter will be sent to a candidate summarizing the research study from the patient's provider including ways the patient can contact the study team to indicate that she is not interested in pursuing the study further. This will be in the form of informational letters or emails, and patients will be called by a member of the study staff for screening. Subjects will receive \$20 in compensation for each of the three study assessments. Compensation will be given in the form of gift cards.

Clinicians. Clinicians have been identified from the FCCC gynecologic cancer clinical team. We will enroll between 3-6 FCCC gynecologic cancer clinicians (gynecologic/radiation oncology). Clinicians will be

approached to participate in the study via clinical meetings either in-person or virtually, or through direct contact with [name] (Co-I), [name] (PI), or another study team member. Interested clinicians will be sent a link to online consent forms for self-enrollment. Clinicians will be compensated a total of \$20 for participating, to complete a brief socio-demographic study survey, and to review the materials we are providing them about menopausal and sexual health concerns after gynecologic cancer. Compensation will be in the form of gift cards.

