8.0 Intervention Conditions

8.1. Starting the Conversation. The STC intervention consists of a 25-minute video accessible via smartphone, computer or tablet, and an accompanying 5-page workbook providing information and targeted skills training for communicating with providers about sexual concerns. In addition, women will receive a 2-page resource guide consisting of information about institutional and external resources on sexual and menopausal health related to gynecologic cancer and its treatment.³⁰ The video includes a slideshow with narration and will be made available through a link sent to participants via email; the workbook in paper format and will be sent via mail. All participants will be sent the resource guide several weeks prior to an upcoming scheduled clinic visit with instructions to read it prior to their visit. Women in the STC intervention arm will also be sent a link via email to the video with instructions to watch the video and complete the exercises in the accompanying workbook prior to their upcoming visit. Participants in both conditions will receive a reminder call close to their scheduled visit, and those who have not reviewed materials close to their visit will be offered the opportunity to come early to their visit and view the materials using a study tablet immediately prior to their clinic encounter in a private space.

STC intervention content was initially developed based on formative qualitative work with breast cancer patients and clinicians on knowledge and skills gaps and intervention preferences⁸⁴ and by principles of social cognitive theory,⁵⁹ which emphasize building self-efficacy through learning skills for effectively discussing sexual health concerns. Menopausal issues were also included because the treatments commonly given to women with hormonal-dependent breast cancer eliminate estrogen (e.g., aromatase inhibitors, chemotherapy, ovarian suppression) and therefore cause both distressing sexual and menopausal symptoms.¹⁰⁴⁻¹⁰⁷ To maintain consistency with the initially tested intervention while enhancing relevance for gynecologic cancer, we include menopausal issues but focus on genito-urinary symptoms of menopause (e.g., vaginal symptoms, urinary symptoms), since they tend to be highly associated with women's sexual function difficulties.^{4,39}

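### One published block size of six at 2:1, with no stated barrier between recruiting staff and past assignments, leaves the claimed limit on prediction weakened and not assured.

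*Combined protocol and SAP*

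**What the plan says.** Section 7.0 (Randomization) states that "patients will be randomized with an allocation ratio of 2:1 to either the STC intervention" or to control, and that the statistician generates the sequence through an "automated randomization procedure in REDCap that limits prediction of allocation and protects masking of allocations". Section 19.0 repeats that assurance. Section 7.0 gives one block size: "Randomization in blocks of six will guarantee that, after every six assignments, the study arms will have equal numbers". It mentions no stratification, no second block size and no withholding of the size.

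On timing: "Randomization will occur once the patient has consented and completed the baseline (T1) survey". On disclosure: "The automated randomization function in REDCap will inform the Research Lab Manager of the patient's assigned treatment condition". No other role is named as receiving assignments. Section 19.0 masks the data analyst and nobody else.

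The arms differ openly. Under 8.1, "Women in the STC intervention arm will also be sent a link via email to the video" and are mailed a workbook; under 8.2, control women receive the resource guide alone. Section 8.1 also provides reminder calls and in-clinic viewing for women who have not reviewed their materials, without saying which staff do this. On recruitment, 4.2 says "The research assistant will ask the providers' permission to approach patients identified as medically eligible", and 4.4 has the research assistant screen by telephone, with in-person approach as an alternative. Section 15.0 marks multi-site research as not applicable, although 17.0 refers in passing to both recruiting sites.

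**The concern.** In a permuted block of known size, once one arm's quota is used up the rest of the block is known. With four STC and two control places, that happens as soon as two controls or four STC women have been assigned. A person who keeps count then knows the next assignment before the next woman completes her baseline survey.

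This matters because staff have discretion, and prognostic information, before randomization. They pre-screen charts, seek provider permission, choose whom to call or approach, and record a 0-10 sexual-concern score at screening. If someone doing this work also knew the next slot, the order of approach, or how hard a woman is pressed to finish T1, could differ by arm. The resulting imbalance would enter the STC-control contrast in self-efficacy, communication and sexual function, with about 20 and 10 women. Section 16.1.2.3 reports these outcomes descriptively but says the results will inform power calculations for the definitive trial.

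**Working it through.** **Inputs.** Ratio 2:1 and block size 6 (7.0); 30-36 patients, 20-24 STC and 10-12 control (16.1.2); decision rules applied to the first 30 participants, with at least 14/20 and 15/20 on the STC arm (Table 4).

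**The plan's own figures.** A block of six at 2:1 holds 4 STC and 2 control. Five blocks give 20:10 and six give 24:12, as stated. Table 4 also reproduces where it depends on the split: P(at least 14 of 20 at 80%) = 91.3% and P(at least 15 of 20 at 85%) = 93.3%, against the stated 91% and 93%. The plan gives no figure for predictability.

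**Certain assignments per block.** There are C(6,2) = 15 equally likely orderings. A slot is certain when one arm's quota is already used up.

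| Position | Orderings in which the slot is certain | Probability |
|---|---|---|
| 1, 2 | 0 | 0 |
| 3 | 1 (both controls in the first 2) | 6.7% |
| 4 | 3 (both controls in the first 3) | 20.0% |
| 5 | 6 + 1 (both controls, or all four STC, in the first 4) | 46.7% |
| 6 | 15 | 100% |

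Sum: (1 + 3 + 7 + 15)/15 = 26/15 = 1.733 of 6 = 28.9%. The closed form agrees: 4/(2+1) STC + 2/(4+1) control = 1.333 + 0.400 = 1.733.

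- Over 30 women: 5 × 1.733 = 8.7 certain (6.7 STC, 2.0 control).
- Over 36 women: 6 × 1.733 = 10.4.
- Best guess from the history, by enumeration: 74.4% correct, against 4/6 = 66.7% from always guessing STC.

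These figures apply to an observer who knows the block size, the block boundaries and all earlier assignments. Without that history no assignment is certain. If the equal-numbers sentence were taken literally as 3:3, the certain share would be 1.5/6 = 25%; the conflict between that sentence and 2:1 is a separate matter.

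**Effect of varying the block size.** Simulated, allowing the observer to know the possible sizes and all past assignments:

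- *Unconstrained.* With equally likely blocks of 6 and 9 the certain share is about 6%; with 3, 6 and 9, about 3%. But the first 30 then contain something other than 20 STC women about 26% and 22% of the time. With 19 STC, the same 70% and 75% thresholds require 14 (0.70 × 19 = 13.3) and 15 (0.75 × 19 = 14.25), and the probability of success under the favorable condition falls from 91% to 84% and from 93% to 86%.
- *Constrained to sum to 30.* The first 30 are always 20:10. The certain share is about 7-12%, depending on the sizes used, even if the observer also knows the total. Best-guess accuracy is about 73-75%, so it hardly moves.

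**The case against.** The other side has a good case on several points.

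- **Who knows.** A reader might infer that the whole recruiting team sees every assignment. The documents do not say so: only the Research Lab Manager is named, and mailing and reminder calls are described without roles. Arm-specific delivery makes wider knowledge plausible, no more. This point stands.
- **What is claimed.** A reader might also conclude that the stated protection fails outright. The text says prediction is limited, not prevented, and about 71% of assignments stay uncertain even to a fully informed observer. Most of the certain slots are STC (1.33 of 1.73), which is already the two-in-three guess; only about 2 of 30 are known control slots. This stands too.
- **Steering is hard.** A slot is filled when T1 is completed, after provider permission, a letter with opt-out, a call, consent and a mostly online survey. Knowing the next slot does not put a chosen woman in it. This makes steering less likely, but selective approach and uneven chasing of T1 remain possible.
- **Limited consequence.** Enrollment and retention are pooled, completion and acceptability are STC-only, and 16.1.2.3 rules out formal testing. The primary decision rules are therefore not arm comparisons. The effect sizes carried into planning the larger trial are still exposed.
- **A naive fix does harm.** Freely varied block sizes would disturb the 20 STC women on whom Table 4 rests. That is correct, and it is why the sizes need to be constrained.

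**Conclusion.** The concern holds in a limited form. The plan asserts that prediction of allocation is limited, prints the one fact that most helps prediction, and names no safeguard between past assignments and the staff who recruit. For someone with the full history, 28.9% of assignments (about 8.7 of 30) are certain. The size of any resulting bias cannot be derived from the documents, and nothing in them shows that selective recruitment would occur, so the supported statement is that the STC-control effect sizes could be biased.

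The conclusion rests on 4:2 blocks throughout, no stratification, and an observer who tracks every assignment; whether a recruiter is such an observer is not stated. The fault does not invalidate the pilot, but it is worth correcting because the correction is cheap and these estimates feed the next trial.

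**What to change.** 1. Have the statistician load into REDCap a 2:1 list with randomly ordered block sizes in multiples of three (for example 3, 6 and 9), constrained to sum to 30. The first 30 stay at 20:10 and the 14/20 and 15/20 rules in Table 4 are unchanged. Add a further block or blocks of 3 or 6 for participants 31-36.
2. Remove the block size from section 7.0 and hold it with the statistician only.
3. State in 7.0 and 19.0 that staff who screen, approach and consent patients do not see past assignments or running arm totals, and name the roles that send arm-specific materials and make reminder calls.

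The third step matters most. Varying the sizes cuts certain slots to about 7-12% but leaves best-guess accuracy near 73-75%; withholding the history leaves a recruiter with no certain slot and only the 66.7% guess.

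The cost is a new allocation table and a sentence or two of protocol text. The split may be off by one or two women if enrollment stops mid-block. At one center with a small team, separating the roles in step 3 may take some reassignment of tasks.
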